5.2 RANDOMIZATION

Subjects who meet all inclusion criteria and no exclusion criteria and who consent to participate in the study will be randomized in a 1:1 ratio to receive either incisional NPWT via PIMS or ActiV.A.C or the standard-of care dressing following surgery. Randomization may occur up to 5 business days prior to surgery. If a subject is randomized and surgery is subsequently delayed, they will not be re-randomized even if outside the 5-day window.

Randomization will be stratified according to surgical site (colorectal vs hepatopancreatobiliary) and body mass index (BMI), < 30 vs ≥ 30.

Randomization using permuted block scheme will be done via REDCap Randomization Application. Please refer to the randomization manual for detailed instructions.

6.0 SUBJECT SELECTION

6.1 INCLUSION CRITERIA

1. Female and male patients 18 years of age or older
2. Scheduled for an elective surgery in either open CRS or open HPBS. This includes, but is not limited to: ileocecectomy, right hemicolectomy, extended right hemicolectomy, transverse colectomy, left hemicolectomy, sigmoidectomy, proctectomy, low anterior resection or abdominoperineal resection, hepatectomy, bile duct reconstruction, duodenectomy, pancreatectomy, pancreaticoduodenectomy, or pancreatic duct reconstruction

6.2 EXCLUSION CRITERIA

1. The need for emergency surgery.
2. The need for use of only laparoscopic surgery. Note: Hand-assisted laparoscopic procedures are not exclusionary. Patients scheduled for a staging laparoscopy followed by an open procedure are permitted to participate.
3. Presence of bowel obstruction, strangulation, peritonitis or perforation.
4. The presence of local or systemic infection preoperatively.
5. ASA class ≥4.
6. Inability to provide informed consent and authorization.
7. Known allergy or hypersensitivity to silver.
8. Patients who are pregnant
9. Any clinically significant condition that, in the investigator's opinion, would significantly impair the subject's ability to comply with the study.

6.3 INCLUSION OF WOMEN AND MINORITIES

Men and women of all races and ethnic groups are eligible for this trial.

7.0 STUDY ASSESSMENTS

7.1 STUDY CALENDAR

	Baseline ^a	Cycle Day		
		Day of Surgery	Post-op Visit 4-5 days	Post-op Visit 30 days (+/-14)
Informed Consent	X			
Demographics	X			
Medical and Surgical history	X			
Physical Exam and Vital Signs	X			
Pregnancy Test ^b	X			
Randomization ^c		X		
Incisional NPWT via PIMS or ActiV.A.C or standard wound application ^d		X		
Incision Assessment			X	X
Adverse Event Assessment		Throughout Study		
Concomitant Medication	X			

a: Screening procedures will be performed within 42 days prior to surgery.

b: Serum or urine pregnancy test in women of childbearing potential will be performed within 30 days prior to surgery

c: Randomization may occur within 5 business days of surgery.

d: Wound application will be done in the operating room by the OR team.

7.2 SCREENING AND BASELINE EVALUATIONS

All baseline assessments must be done within 42 days of surgery.

- Physical Exam and vital signs
- Medical History
- Surgical History
- Concomitant Medications (must be done or confirmed on the day of surgery): Include a list of pre-treatment chemotherapy and/or radiation for rectal cancer patients. Also include antibiotics within 30 days prior to surgery, steroid use within 1 week prior to surgery, medications related to anticoagulation within 30 days prior to surgery.

A serum or urine pregnancy test will be conducted on women of childbearing age within 30 days prior to surgery.

Eligibility will be reviewed by two key personnel prior to randomization to ensure eligibility (inclusion and exclusion) criteria have been met. The PI will review final eligibility prior to surgery.

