5.0 STUDY DESIGN

5.1 STUDY DESCRIPTION

This study is a multi-center, open-label, randomized clinical trial conducted at Duke Cancer Institute and Indiana University to evaluate whether incisional NPWT can help reduce the rate of SSI in patients undergoing either colorectal or hepatopancreatobiliary surgery. Up to 170 subjects will be randomized in a 1:1 ratio to either conventional wound care (control group) or the incisional NPWT (experimental group) to ensure 138 evaluable subjects.

The primary study endpoint will be SSI within the laparotomy wound, as assessed on postoperative day 4-5 and the first postoperative clinic visit, which is anticipated to be within 30 days of surgery. Evaluable subjects are defined as those who have been randomized and completed both postoperative assessments. Non-evaluable subjects are those subjects who were randomized but did not complete both post-op visits. Non-evaluable scenarios include aborted surgeries, cancelled surgeries, death unrelated to study, and early device removal related to device malfunction. Screen failures are defined as those subjects not randomized.

Safety endpoints will be adverse events related to the device or dressing, including the presence of any abnormal skin findings (such as blisters or rash). These endpoints will be assessed from the day of surgery through the 30-day follow-up visit.

Subjects randomized to conventional wound care (control group) will have their skin incisions closed with skin staples, sutures, or surgical glue (per judgment of the treating physician), covered with sterile medical gauze and a form of adherent (tape or clear adhesive) for which the subject does not have any allergy. This dressing will be removed per the treating physician's discretion or institutional standards.

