10.1 STATISTICAL ANALYSIS

The primary analysis will include all randomized and evaluable patients but exclude ineligible patients or patients who are canceled from the study before receiving any wound care. SSI is defined as an infection that occurs within 30 days of operation. The primary endpoint is the SSI rate. The primary analysis of comparing the conventional wound care (control group) and the incisional V.A.C® (experimental group) will be conducted using a chi-square test for two-sample binomial probabilities with a one-sided significance level of 0.1. The observed SSI rates and 90% Upper Confidence Bound (UCB) estimates will be reported. Preoperative, intraoperative, and postoperative variables will be tabulated and appropriate summary statistics will be reported. As a secondary analysis, comparison of treatment groups for SSI will be adjusted for any significant preoperative, intraoperative, or postoperative variables using logistic regression.

For secondary endpoints, the incidence of SSI as superficial incisional, deep incisional, and organ/space will be estimated along with the 90% UCBs. The secondary endpoint length of stay is a continuous variable. A Wilcoxon rank sum test will be used to assess the significance of the difference between groups in median length of stay. Median length of stay, its range and quartiles will be reported.

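### Section 10.1 drops ineligible patients from an open-label primary analysis with no deadline, no masking and no limit to pre-randomisation facts, and Section 7.2 allows the final eligibility review to follow randomisation

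*Combined protocol and SAP*

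**What the plan says.** - **Analysis set (Section 10.1).** "The primary analysis will include all randomized and evaluable patients but exclude ineligible patients". The full exclusion clause is to "exclude ineligible patients or patients who are canceled from the study before receiving any wound care". It names no decision-maker, deadline, evidence standard or masking. No as-randomised analysis is planned, even as a sensitivity analysis.
- **Eligibility checks (Section 7.2).** There are two, with different deadlines. "Eligibility will be reviewed by two key personnel prior to randomization to ensure eligibility (inclusion and exclusion) criteria have been met". Then: "The PI will review final eligibility prior to surgery". In the same section, one baseline item can be completed late: "Concomitant Medications (must be done or confirmed on the day of surgery".
- **Timing (Section 5.2).** "Randomization may occur up to 5 business days prior to surgery". Also: "If a subject is randomized and surgery is subsequently delayed, they will not be re-randomized even if outside the 5-day window". The study calendar and Section 7.3.2 list randomisation under the day of surgery, with the 5-business-day window as an allowance.
- **Masking (Section 5.1).** "This study is a multi-center, open-label, randomized clinical trial". No section keeps the PI unaware of the arm during the eligibility review.
- **Expected losses (Section 10).** The sample size allows for 14% ineligible or non-evaluable patients, as one pooled figure. At the time of the revision 143 patients were enrolled, and up to 27 more were to be added to reach 170.

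**The concern.** A late eligibility check does no harm if everyone randomised and operated on is analysed. An exclusion for ineligibility does little harm if it rests on facts fixed before allocation and is judged blind to arm. This plan has neither safeguard, and the two sections together leave a gap: the final review may take place when the arm is known, and Section 10.1 attaches an analysis consequence to ineligibility.

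Several exclusions in Section 6.2 call for judgement or can change in the days before surgery: bowel obstruction, peritonitis or perforation (3), local or systemic infection (4), ASA class (5) and the investigator-opinion criterion (9). These plausibly relate to SSI risk. If such patients were removed more readily from one arm, the SSI difference would be biased and the one-sided 0.1 error rate would no longer hold.

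**Working it through.** **1. The plan's own figure.** Inputs from Section 10: control 17%, experimental 5%, one-sided alpha 0.1, 1:1 allocation, 170 enrolled, 14% loss. Power = Φ[(d − z·SE0)/SE1], with d = 0.17 − 0.05 = 0.12, z = 1.2816, SE0 = √(2 × 0.11 × 0.89/n) and SE1 = √((0.17 × 0.83 + 0.05 × 0.95)/n).

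- 170 × 0.86 = 146, so n = 73 per arm: SE0 = 0.0518, SE1 = 0.0508, power = Φ(1.055) = 0.854.
- 138 evaluable (Section 5.1), so n = 69 per arm: SE0 = 0.0533, SE1 = 0.0523, power = Φ(0.99) = 0.839.

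Both agree with the stated figure of approximately 85%. The sample size is not in dispute.

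**2. The sequence the text allows.** Two staff confirm eligibility. The patient is randomised, and the arm can be known. Five business days or more may pass. The PI carries out the final review before surgery. At analysis, ineligible patients are dropped. Nothing in Sections 5.2, 7.2 or 10.1 prevents that order.

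**3. How many patients could be affected.** 170 × 0.14 = 23.8, about 24 patients. This pools ineligible with non-evaluable patients, and Section 5.1 lists causes of non-evaluability that have nothing to do with eligibility (cancelled or aborted surgery, unrelated death, device malfunction). The ineligible part, and its split by arm, cannot be recovered from the documents.

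**4. Effect on the error rate, under assumptions.** The documents supply the 11% overall SSI rate and 85 per arm. The following are assumed: no true effect, k patients removed from the NPWT arm only, and removed patients with SSI risk r. The NPWT rate among those left is (85 × 0.11 − k·r)/(85 − k). For example, k = 4 and r = 0.50 gives (9.35 − 2.00)/81 = 0.091. The rejection probability is the exact binomial probability that the pooled two-proportion z statistic exceeds 1.2816 in favour of NPWT.

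| Removed from NPWT arm | r = 17% | r = 20% | r = 30% | r = 50% |
|---|---|---|---|---|
| 0 | 0.098 | 0.098 | 0.098 | 0.098 |
| 2 | 0.109 | 0.111 | 0.121 | 0.143 |
| 4 | 0.111 | 0.117 | 0.139 | 0.191 |

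Part of the smallest increases comes from the discreteness of the test: removing 2 or 4 patients of average risk (r = 11%) gives 0.103 and 0.100. In these cases removal depends on prognosis and arm, not on the SSI outcome, which is all that a review before surgery could act on.

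**The case against.** The case on the other side is substantial, and much of it stands.

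- **The PI's review need not follow randomisation.** A reader might infer from Section 7.2 that it does. The text says only that it precedes surgery, and a PI review before randomisation would comply. Section 5.2 randomises only patients who already meet all criteria, and the calendar puts randomisation on the day of surgery by default. So the order is permitted, not prescribed.
- **The link to Section 10.1 is not written down.** No section says that the PI's review decides who counts as ineligible for the analysis, or that the PI knows the arm at that point. Open-label conduct makes this possible, no more. The same silence also means that nothing rules it out.
- **A single removal could be shown to overturn the result.** For example, 10/69 v 5/69 gives z = 1.37 and one-sided p = 0.086, while 10/69 v 6/70 gives z = 1.09 and p = 0.137. A reader might take this as the size of the problem. It is not: it removes a treated patient after the SSI is known, which a review before surgery cannot do, and the counts were chosen to straddle 0.1.
- **The wound-care condition in 10.1 may cover both groups.** It most naturally attaches to cancelled patients, but it can be read as applying to ineligible patients too. On that reading no treated patient is removed. Arm-aware removal between randomisation and surgery would still be possible.
- **Few patients may be involved.** Two staff have already checked eligibility, so later findings may be rare. This limits the likely size. It does not close the route.

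**Conclusion.** The point holds as a gap in the plan. Section 10.1 permits ineligibility exclusions that are made after allocation, with the arm known, at no fixed time and on facts that may have arisen after randomisation. Section 7.2 makes one such occasion available.

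The documents do not support saying that any arm-dependent exclusion has occurred, that the PI's review must follow randomisation, or that all of the 14% is exposed to this.

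The size is conditional. With no true effect, 11% SSI, 85 per arm and all of 2 to 4 removals from the NPWT arm, the one-sided error moves from about 0.10 to about 0.11-0.12 at 17-20% risk in those removed, and to about 0.12-0.19 at 30-50%. Neither the one-sided removal nor the risk range comes from the documents. The first range is modest, and the second would matter. The point should be fixed because the remedy is cheap. It belongs mainly to Section 10.1, which governs every patient, rather than to Section 7.2.

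**What to change.** **Main change, Section 10.1.** Define the primary analysis as all randomised patients who undergo the laparotomy and have SSI assessed, analysed in the assigned arm, whatever is found about eligibility after randomisation. This must include a patient declared ineligible between randomisation and surgery who still has the operation; a rule tied only to receipt of study wound care could leave that patient out. Report ineligibility findings by arm, reason and timing. Keep the present exclusion rule as a sensitivity analysis. The new wording should also be squared with Section 5.1, which requires both postoperative assessments for evaluability.

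**Secondary change, Section 7.2.** Require the PI's eligibility sign-off before randomisation. This reaches at most 27 of 170 patients (16%), so it cannot replace the first change.

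**Cost.** A short amendment to two sections, an existing review moved earlier by a few days, and one additional table. A few ineligible patients stay in the primary analysis, which may slightly dilute the effect.

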7.3 EVALUATIONS DURING STUDY

7.3.1 Throughout Study

- Adverse Event evaluation specific only to the NPWT units and dressings unit (e.g. blistering, redness)

7.3.2 Day of Surgery

- Randomization (or within 5 business days of surgery)
- NPWT via PIMS or ActiV.A.C. or standard of care wound application; application will be done in the operating room by the OR team.

7.3.3 Post-op Visit Day 4-5

- Post-operative incision assessment
- Review of any side effects or symptoms
- This may be conducted by a review of clinical data
- PI will confirm the clinical data of any finding indicative of infection (i.e. redness, fever, positive culture)

7.3.4 Post-op Visit Day 30 (+/-14)

- Post-operative incision assessment
- Review of any side effects or symptoms
- This may be conducted by a review of clinical data

- PI will confirm the clinical data of any finding indicative of infection (i.e. redness, fever, positive culture)

8.0 CLASSIFICATION OF SSI BY NSQIP

The following definitions will be used to classify SSI:

Superficial Incisional SSI: Superficial incisional SSI is an infection that occurs within 30 days after the operation *and* infection involves only skin or subcutaneous tissue of the incision *and* at least *one* of the following:

- Purulent drainage, with or without laboratory confirmation, from the superficial incision.
- Organisms isolated from an aseptically obtained culture of fluid or tissue from the superficial incision.
- At least one of the following signs or symptoms of infection: pain or tenderness, localized swelling, redness, or heat AND superficial incision is deliberately opened by the surgeon, unless incision is culture-negative.
- Diagnosis of superficial incisional SSI by the surgeon or attending physician

Deep Incisional SSI: Deep Incision SSI is an infection that occurs within 30 days after the operation and the infection appears to be related to the operation and infection involved deep soft tissues (for example, fascial and muscle layers) of the incision and at least one of the following:

- Purulent drainage from the deep incision but not from the organ/space component of the surgical site.
- A deep incision spontaneously dehisces or is deliberately opened by a surgeon when the patient has at least one of the following signs or symptoms: fever ($> 38^{\circ}$ C), localized pain, or tenderness, unless site is culture-negative.
- An abscess or other evidence of infection involving the deep incision is found on direct examination, during reoperation, or by histopathologic or radiologic examination.
- Diagnosis of a deep incision SSI by a surgeon or attending physician.
- Report infection that involves both superficial and deep incision sites as deep incisional SSI.

Organ/Space SSI: Organ/Space SSI is an infection that occurs within 30 days after the operation and the infection appears to be related to the operation *and* the infection involves any part of the anatomy (for example, organs or spaces), other than the incision, which was opened or manipulated during an operation *and* at least *one* of the following:

- Purulent drainage from a drain that is placed through a stab wound into the organ/space.
- Organisms isolated from an aseptically obtained culture of fluid or tissue in the organ/space.
- An abscess or other evidence of infection involving the organ/space that is found on direct examination, during reoperation, or by histopathologic or radiologic examination.

- Diagnosis of an organ/space SSI by a surgeon or attending physician.

Do not report the following conditions as SSI:

- Stitch abscess (minimal inflammation and discharge confined to the points of suture penetration).
- Infected burn wound.

9.0 SUBJECT DISCONTINUATION

Subjects may withdraw from this study at any time.

Reason for discontinuation from the trial will be recorded.

The Principal Investigator may discontinue a subject from the protocol regimen. Reasons for subject discontinuation by the investigator may include but are not limited to the following:

- Death
- Investigator or PI determination that it is not in the subject's best interest to continue participation
- Lost to follow-up

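### Section 9 does not require SSI status to be obtained after an investigator discontinuation, and the completers-only primary analysis then drops subjects whose assessment is missing

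*Combined protocol and SAP*

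**What the plan says.** Section 5.1 describes the design: "This study is a multi-center, open-label, randomized clinical trial". The treating team and the investigator therefore know the arm.

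Section 9.0 gives the discontinuation rule in two different terms. It opens with "The Principal Investigator may discontinue a subject from the protocol regimen", which concerns treatment. One of the listed reasons is "Investigator or PI determination that it is not in the subject's best interest to continue participation", which concerns being in the trial at all. The other listed reasons are death and loss to follow-up, and the list is expressly open-ended. The only stated data requirement is "Reason for discontinuation from the trial will be recorded".

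Two other sections determine what happens to such a subject in the analysis:

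- Section 5.1: "Evaluable subjects are defined as those who have been randomized and completed both postoperative assessments", and "Non-evaluable subjects are those subjects who were randomized but did not complete both post-op visits".
- Section 10.1 (the end of the sentence, cut here, refers to treatment of the wound): "The primary analysis will include all randomized and evaluable patients but exclude ineligible patients or patients who are canceled from the study before receiving any".

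Three provisions soften this. Sections 7.3.3 and 7.3.4 say of the day 4-5 and day 30 assessments: "This may be conducted by a review of clinical data". Section 5.1 leaves the duration of NPWT, between 2 and 7 days, to the physician. Section 11.0 says that a loss of negative pressure does not decide evaluability.

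**The concern.** Objective 4.1 compares SSI between the randomised arms. The analysis instead compares those subjects in each arm for whom both assessments were completed. That is harmless if missing assessments are unrelated to arm and wound status. Section 9 leaves open a route by which they may be related: a person who knows the arm judges that a subject should not continue, and nothing then obliges anyone to establish whether an SSI developed.

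The opportunity may differ by arm. The NPWT arm has a defined device regimen of several days. The control dressing comes off at the physician's discretion or by institutional standards. If early wound trouble prompts discontinuation more often in one arm, SSI cases are lost selectively from that arm. Few events are expected, so a small number of lost cases matters. The plan gives no all-randomised analysis, no rule for missing SSI status and no sensitivity analysis that would reveal the effect.

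**Working it through.** **Inputs from the documents.** Control rate 17%, NPWT rate 5%, one-sided level 0.1, power about 85%, up to 170 subjects allocated 1:1, 14% ineligible or non-evaluable, and a pooled observed SSI rate of 11% (all Section 10.0). Section 5.1 gives 138 evaluable subjects. Applying the 14% gives 170 x 0.86 = 146, or 73 per arm. The 138 gives 69 per arm.

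**Step 1: reproduce the plan's power.** With p1 = 0.17, p2 = 0.05 and mean 0.11:

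power = Φ{[0.12 - 1.2816 x √(2 x 0.11 x 0.89/n)] / √[(0.17 x 0.83 + 0.05 x 0.95)/n]}

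- n = 73: (0.12 - 0.0664)/0.0508 = 1.055, power 85.4%.
- n = 69: (0.12 - 0.0683)/0.0523 = 0.990, power 83.9%.

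The stated figure of about 85% is confirmed, so the uncorrected one-sided chi-square is used below.

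**Step 2: sensitivity of a planned-looking result.** Expected counts at 73 per arm are 0.17 x 73 = 12.4 and 0.05 x 73 = 3.65. Take 12/73 v 4/73. The pooled rate is 16/146 = 0.1096, z = 0.1096/0.0517 = 2.12, p = 0.017. Now restore k SSI cases that had been dropped:

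| k | NPWT only | p, NPWT only |
|---|---|---|
| 0 | 4/73 | 0.017 |
| 1 | 5/74 | 0.033 |
| 2 | 6/75 | 0.058 |
| 3 | 7/76 | 0.093 |
| 4 | 8/77 | 0.138 |

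Restoring four cases to each arm (16/77 v 8/77) gives p = 0.038.

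On the rate scale, (3.65 + 1)/(73 + 1) = 6.3%. One restored NPWT case therefore moves the rate by 1.3 points, about 11% of the assumed 12-point effect.

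**Step 3: type I error.** Assume a true rate of 11% in both arms. If a fraction s of SSI cases is lost from an arm, the rate among those kept is 0.11(1 - s)/(1 - 0.11s). Exact enumeration of the test gives the table below. In the fourth column, the lower figure lets the NPWT arm shrink by the lost cases and the higher one holds it at 73.

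| s (assumed) | NPWT cases lost, 73 x 0.11 x s | Rate among those kept | Loss in NPWT only | Equal loss in both arms, 73 held |
|---|---|---|---|---|
| 0 | 0 | 11.0% | 10.7% | 10.7% |
| 10% | 0.8 | 10.0% | 14-15% | 10.7-10.8% |
| 20% | 1.6 | 9.0% | 19-20% | 10.7-10.8% |
| 30% | 2.4 | 8.0% | 26-27% | 10.7-10.8% |

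The test already runs slightly above 0.1 with no loss, because the counts are discrete. The rise above 10.7% is what selective loss adds.

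**The case against.** The strongest reply is that discontinuation need not cost an outcome. Much of that reply stands.

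- A reader might infer that Section 9 ends SSI follow-up. It does not: it is silent. Evaluability depends on the two assessments, not on staying on the regimen, and both may be made from clinical data. A discontinued subject can therefore remain evaluable. What is missing is any requirement to do this for discontinued subjects, so practice could vary by site and case.
- A reader might infer that stopping the device over a worrying wound removes the subject. Stopping between days 2 and 7 is within Section 5.1 and does not in itself make anyone non-evaluable. Section 5.1 names early device removal as non-evaluable only when it is due to malfunction. That scenario is a separate matter, to be reconciled with Section 11.0.
- A reader might infer that the bias favours NPWT. Section 9 applies to both arms, and Step 3 shows that equal loss does almost nothing. The harm needs loss that differs by arm, and the direction is not documented.
- The loss fractions have no source. The 14% in Section 10.0 combines ineligible and non-evaluable subjects and gives no reasons. Losing significance in Step 2 needs four lost cases against four observed, so half of all NPWT infections would have left by this route. That is an extreme case.

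What survives is narrower: a discretionary exit known to be open-label, no duty to ascertain the outcome afterwards, and an analysis set that drops whoever is then missing.

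**Conclusion.** The point holds in conditional form. The documents permit an outcome-related and arm-related loss from the primary analysis, and they contain nothing that would prevent or reveal it. They do not show that any subject was lost this way.

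If SSI cases were lost from the NPWT arm only, a loss of one to two cases would raise the false-positive rate from 10.7% to between about 14% and 20%. This rests on an assumed 11% rate in both arms, about 73 evaluable per arm and assumed loss fractions. With equal loss in both arms there is no material inflation. This is a worthwhile, inexpensive tightening of the plan, not evidence that the trial's result is biased.

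**What to change.** In Section 9, add that discontinuing the assigned dressing or regimen, for any reason, does not end SSI ascertainment, and that SSI status through day 30 is obtained by review of clinical data unless the subject withdraws consent for data use. This changes what is recorded, not how any patient is treated.

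In Section 10.1, add that these subjects are analysed in their randomised arm, that the number with unknown SSI status is reported by arm, and that a tipping-point analysis is run over those subjects.

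The cost is a few sentences in an amendment. Chart review is already an accepted form of both assessments, so no new visit is needed. Power does not suffer from the numbers retained: by the Step 1 formula it is 83.9% at 69 per arm and 89.3% at 85 per arm. The latter is an upper bound, since cancelled or aborted operations still cannot contribute. The one downside is slight dilution of the effect from subjects with partial NPWT exposure. Section 10.0 reports that no analysis of the endpoint had been conducted at the time of the amendment, so on that text the rule could still be fixed before the arms are compared.
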